11.2.3 UPPER AND LOWER EYELID RETRACTION BASED ON MRD1 AND MRD2

Eyelid retraction is defined as a displacement of the upper eyelid superiorly or lower eyelid inferiorly. Measurements consist of the MRD1 (margin reflex distance 1; upper lid) and MRD2 (margin reflex distance 2; lower lid) in mm. Measurements are assessed at all visits according to the schedule of assessments. The assessments will be presented in listings.

CONFIDENTIAL

The contents of this document are confidential to [REDACTED]
Unauthorized use, disclosure, or reproduction is strictly prohibited.

11.2.4 LID APERTURE

Lid aperture is defined as the distance between the lid margins in millimeters with the patient looking in the primary position, sitting relaxed and with distant fixation. Lid aperture will be based on lid aperture measurements, which will be presented in listings.

11.2.5 DIPLOPIA USING THE BAHN-GORMAN SCALE

Diplopia, or double-vision, will be assessed with the Bahn-Gorman Scale with the following responses:

- Grade 0 – No diplopia present
- Grade I – Intermittent diplopia: present only when patient is fatigued
- Grade II – Inconstant diplopia: present only on lateral or upward gaze
- Grade III – Constant diplopia: present on straight and level gaze and correctable with prisms
- Grade IV – Constant diplopia: present on straight and level gaze but not correctable with prisms

Diplopia is assessed at all appropriate visits according to the schedule of assessments. The assessments will be presented in listings.

11.2.6 LAGOPHTHALMOS AND VON GRAEFE'S SIGN

Presence or absence of lagophthalmos and Von Graefe's Sign are assessed at the appropriate visits according to the schedule of assessments. The assessments will be presented in listings.

11.2.7 EXTRAOCULAR MOVEMENTS

Extraocular movements in all 4 primary directions (up, down, nasal, and temporal) will be performed at all appropriate visits according to the schedule of assessments and will be recorded in degrees using the Hirschberg method. Adduction (inward or medial movement toward the nose), abduction (outward or lateral movement toward the ear), supraduction (upward vertical rotation around the horizontal axis), and infraduction (downward vertical rotation around the horizontal axis) will be recorded. The assessments will be presented in listings.

11.3 Analysis of the Exploratory Efficacy Variables

11.3.1 ORBITAL IMAGING AND FACIAL PHOTOGRAPHY FROM CENTRAL READING CENTER

Axial high-resolution images will be obtained locally and transmitted to a central radiology vendor for review. Besides assessment of proptosis, the orbital magnetic resonance imaging (MRI) sequences may provide (but are not limited to) volumetric analysis (in mm³) of orbital compartments such as individual extraocular

CONFIDENTIAL

The contents of this document are confidential to [REDACTED]
Unauthorized use, disclosure, or reproduction is strictly prohibited.

muscle volume and total muscle volume, orbital fat volume, fibrosis measurement of each muscle and average fibrosis of all 4 four muscles per eye. These will be measured at screening and for all visits according to the schedule of assessments and will all be presented as listings. The proptosis listing will include both proptosis readings and the average reading for each visit for the study and fellow eye.

A facial photography assessment will also be done per the ophthalmology manual. Facial photography measurements may be performed and, if present, these will be presented as a listing.

In the US only, an orbital computed tomography (CT) scan may be performed if the patient cannot have an MRI scan.

12. Safety Analyses

All safety analyses will be conducted using the Safety Population. Safety endpoints will be summarized for the LASN01 300 mg, LASN01 600 mg, [REDACTED], placebo, and for the All Patients treatment arms.

12.1 Adverse Events

Treatment-emergent adverse events (TEAEs) are defined as any event that occurs or worsens by clinically meaningful amount on or after the first dose of study drug administration. Only TEAEs will be summarized, however all AEs collected in the eCRF will be presented in data listings. All AEs will be coded using the Medical Dictionary for Regulatory Activities (MedDRA) version as specified in the DMP.

An overall summary will be presented that includes the number of events and the number and percentage of patients who experienced at least one TEAE by treatment arm and overall for all patients. This summary will also include breakdowns of TEAEs further categorized as ocular or non-ocular, serious TEAEs, related TEAEs, TEAEs leading to early treatment discontinuation, TEAEs leading to early study discontinuation, TEAEs leading to death, and Serious TEAEs by maximal severity.

Additional summaries of TEAEs classified by MedDRA SOC and PT will be provided showing the number of events and the number and percentage of patients who experienced at least one TEAE by treatment arm and overall for all patients. If a patient reports multiple TEAEs to the same SOC or multiple PTs within the same SOC, the patient will be counted only once within that SOC or PT. In the summaries, SOC and PTs within the SOC will be listed in descending frequency order for the All Patients column.

Separate summaries by SOC and PT will be provided for the following categories of AEs:

- TEAEs

CONFIDENTIAL

The contents of this document are confidential to [REDACTED]
Unauthorized use, disclosure, or reproduction is strictly prohibited.

- Related TEAEs
- TEAEs by maximal severity grade
- Serious TEAEs by maximal severity grade
- Related TEAEs by maximal severity grade

The number of patients with any TEAEs (along with percentages) will be tabulated by SOC and PT within each SOC by treatment arm and overall for all patients. To count the number of patients with any TEAEs, if a patient has multiple TEAEs coded to the same SOC or PT within an SOC, the patient will be counted once under the maximum severity.

All TEAEs will be presented in a patient listing. In addition, serious TEAEs, related TEAEs, and TEAEs leading to death will be listed separately.

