8.3.1. Time Period and Frequency for Collecting AE and SAE Information

Detection and recording of AEs and SAEs starts from the signing of the ICF until the Day 365/Week 53 visit. From this visit to the EOS visit, only treatment-related AEs/SAEs will be recorded. AEs that occur after signing the ICF, but before the first dose of study drug, will be recorded to the eCRF as medical history, unless related to a study procedure. Detection and recording of TEAEs will start at the time of the first dose of study drug. Any SAE that occurs after signing the ICF (before or after the first dose of study drug) will be recorded to the eCRF as an SAE.

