QTcF	QT Interval Corrected by Fridericia's Formula
RTF	Rich Text Format
SAP	Statistical Analysis Plan
SD	Standard Deviation
SE	Standard Error
SOC	System Organ Class
SRC	Safety Review Committee
$t_{1/2}$	Terminal half-life
TEAE	Treatment-Emergent Adverse Event
TED	Thyroid Eye Disease
T_{last}	Time point with the last measurable concentration
TLF	Tables, Listings and Figures
T_{max}	Time at which the maximal concentration is observed
TSH	Thyroid Stimulating Hormone
TSI	Thyroid Stimulating Immunoglobulin
V_{ss}	Steady-state volume of distribution
V_z	Volume of distribution based on the terminal phase
WHODrug	World Health Organization Drug Dictionary

CONFIDENTIAL

The contents of this document are confidential to [REDACTED]
 Unauthorized use, disclosure, or reproduction is strictly prohibited.

1. Introduction

This statistical analysis plan (SAP) details the planned analyses and reporting for protocol LASN01-CL-2201, with the United States Version 7.0 dated 15NOV2024, and the European and UK Version 7.1 dated 22NOV2024. The statistical methods herein supersede those in the clinical protocol. Any additional required analyses will be completed and identified in the clinical study report.

This SAP has been prepared with consideration of the latest International Conference on Harmonisation (ICH) E9 Guideline, "Guidance for Industry: Statistical Principles for Clinical Trials," and the latest ICH E3 Guideline, "Guidance for Industry: Structure and Content of Clinical Study Reports."

This study was conducted as proof of concept for evaluation of role of IL-11 in thyroid eye disease (TED). TED trials have assigned a target eye, traditional to trials that deliver drug to one eye. As LASN01 is being administered systemically, there should be no difference between either eye and response in either eye should be considered. Procedurally, the protocol has used the target eye as primary endpoint, however, as the study is signal seeking in nature, the drug is administered systemically (intravenously [IV]), and response in either eye is evaluated in consideration of response. A substantial number of patients did not reconsent to protocol v7.0/7.1, which led to the early termination of the study. Only the primary endpoint (proptosis responder) and total 7-point Clinical Activity Score (CAS; Total CAS) endpoints will be summarized. Other exploratory or secondary endpoints will not be analyzed and the per protocol population has been removed.

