3.1 General Study Design

This proof-of-concept Phase 2 study comprises the randomized, double-masked, placebo-controlled treatment arms in patients with TED with no prior anti-IGF-1R treatment [REDACTED]

[figure not shown]
The randomized treatment arms will be used to evaluate the efficacy, safety, tolerability, PK, immunogenicity, and PD properties of 2 dose levels (300 and 600 mg) of LASN01 administered IV Q4W 7 to 13 doses in anti-IGF-1R-naïve patients with TED. [REDACTED]

The general study design for treatment-naïve patients is depicted in Figure 1 for the European protocol version 7.1 and the randomized treatment-naïve patients in the United States protocol version 7.0.

CONFIDENTIAL

The contents of this document are confidential to [REDACTED]
Unauthorized use, disclosure, or reproduction is strictly prohibited.

Figure 1. General Study Design for Treatment-Naïve Patients

Following 49 weeks of dosing (last dose administered on Day 337), patients will be followed for an additional 24 weeks for a total study duration of 73 weeks (End of Study [EOS] visit on Day 505 ±7 days).

Study participation (Baseline to the EOS visit) will require approximately 505 days, not including the Screening period. The Screening visit will occur up to 30 days before Day 1.

Treatment assignments will be performed centrally by [REDACTED]

A Safety Review Committee (SRC) will be formed to periodically review safety and available PK and PD data. For the randomized, double-masked treatment arms, the SRC will examine masked data. The first data review will occur after at least six patients have been treated and followed for six weeks. Subsequent meetings may take place every 12 months, depending on enrollment rates and SRC discussions. The SRC Charter outlines the committee's structure and provides further conduct details. A separate SRC shell will be created to document and confirm SRC outputs.

Interim analysis (IA) may be performed when at least 50% of evaluable patients in the randomized treatment arms complete at least 8 weeks in the study. [REDACTED] The IA will include both masked and unmasked outputs for Sponsor review. A separate unmasked statistician

CONFIDENTIAL

The contents of this document are confidential to [REDACTED]
Unauthorized use, disclosure, or reproduction is strictly prohibited.

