3.2.1 STUDY TREATMENTS

This study will include approximately 36 evaluable patients with TED in 4 treatment arms. Treatment-naïve patients will be randomized (in a 1:1:1 ratio) upon enrollment to LASN01 in either a high-dose (600 mg Q4W ×7-13 doses) or low-dose (300 mg Q4W ×7-13 doses) treatment arm or to placebo. [REDACTED]

[REDACTED] Treatment arms for the randomized and open-label patients are shown in Table 1. The protocol was amended as additional safety data became available to increase the duration of treatment with LASN01.

CONFIDENTIAL

The contents of this document are confidential to [REDACTED]
Unauthorized use, disclosure, or reproduction is strictly prohibited.

Table 1. Multiple Dose Study Design

Randomized Treatment Arm	Dose	Number of Doses	Number of Patients
1	Low-dose LASN01 (300 mg Q4W)	13	8
2	High-dose LASN01 (600 mg Q4W)	13	8
3	Placebo (Q4W)	13	8
Total Number of Patients			24

4. Sample Size

This study will enroll up to 36 evaluable patients with TED across four treatment arms. Approximately 24 patients will be randomized in a 1:1:1 ratio to receive LASN01 600 mg Q4W, LASN01 300 mg Q4W, or placebo.

Randomized Treatment Arms:

- The pooled primary analysis represents a 2:1 randomization of pooled LASN01 (300 mg and 600 mg arms) to placebo with about 24 patients.
- The placebo response rate is assumed to be ~15% (based on Teprotumumab FDA approval data from 2020).
- Assuming a pooled LASN01 response rate of 65% (an absolute treatment effect of 50% over placebo), a sample size of 8 patients per arm provides approximately 81% power at a 10% significance level using a one-sided Fisher's exact test.
- If the placebo response rate is 10%, the power increases to approximately 90% at the same significance level.
- Power calculations were performed using R Version 4.2.1 (R Core Team, 2022), employing simulation methods with 10,000 iterations implemented via the 'statmod' package (Giner, 2016).

CONFIDENTIAL

The contents of this document are confidential to [REDACTED]
Unauthorized use, disclosure, or reproduction is strictly prohibited.

5. Analysis Populations

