10.1 Dosing Compliance

The number of actual doses received will be calculated from the number of infusions recorded in the study drug administration electronic Case Report Form (eCRF). The number of expected doses will depend on which protocol amendment the patient is consented to, regardless of study completion status.

Number of doses received will appear on the Disposition listing; otherwise, study drug administration will have its own listing.

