10.2 Treatment Exposure

Extent of treatment exposure for completed or discontinued patients will be calculated in days using the following:

$$\text{Extent of Exposure (days)} = (\text{Date of Last Dose} - \text{Date of First Dose}) + 1$$

Extent of treatment exposure for each patient exposed to study drug will be summarized with continuous descriptive statistics for each treatment arm, pooled active group (300 mg and 600 mg), and for all patients using the Safety Population.

11. Efficacy Analyses

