Due to several consent withdrawals and patients declining to re-consent for the 12-month extension, the Sponsor unmasked the clinical team to assess whether early study termination was appropriate. Investigators, the CRO clinical operations team, and CRO statisticians remained masked until the database lock. The following specific changes have been made and the additions are considered exploratory:

- Due to early termination of the study, only proptosis measured by Hertel and Total CAS will be analyzed in tables. Other secondary and exploratory endpoints will be listed.
- Either eye responder analyses have been added for proptosis by Hertel and Total CAS, and either eye continuous analyses have been added for Total CAS. Either eye responder and continuous Total CAS analyses will identify an eye at Week 37 (Day 253) and use that same eye in the analysis for each visit.
- A sensitivity analysis, as defined in protocol Section 9.2.4, has been added for Total CAS in the study eye and separately for either eye. Only the pooled active group will be compared to placebo. The sensitivity analysis of the primary responder rate for proptosis from protocol Section 9.4.2. has been removed.

CONFIDENTIAL

The contents of this document are confidential to [REDACTED]
Unauthorized use, disclosure, or reproduction is strictly prohibited.

- An ANCOVA model has been added to existing mean and mean change from baseline Total CAS tables. The model includes baseline and treatment as factors and will be run separately for each eye (study eye and either eye) and visit. Only the pooled active group will be compared to placebo.
- 95% CI for proptosis responder analysis has been removed
- LOCF has been added as the imputation method for missing data for all efficacy analyses.
- Per Protocol Population analyses have been removed.
- ODO analyses have been added for all proptosis and CAS tables to check robustness of results.

17. References

1. Giner G, Smyth GK (2016). statmod: probability calculations for the inverse Gaussian distribution. R Journal 8(1), 339-351.
2. ICH Harmonised Tripartite Guideline: Statistical Principles for Clinical Trials E9. International Council for Harmonisation of Technical Requirements for Pharmaceuticals for Human Use. 05 February 1998.

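### The planned TEAE tables give event counts and crude percentages but no time at risk, although length of follow-up varied between patients

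*SAP*

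**What the plan says.** SAP 12.1 plans an overall TEAE summary giving event counts and "the number and percentage of patients who experienced at least one TEAE by treatment arm", with further tables by system organ class and preferred term, relatedness, seriousness and maximal severity. Protocol 9.2.5 likewise plans plain incidences. Neither section mentions patient-years, an exposure-adjusted rate, time to first event or a common observation window.

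The same SAP describes treatment of unequal length:
- SAP 3.1 has study drug "administered IV Q4W 7 to 13 doses".
- SAP 3.2.1 gives the reason: "The protocol was amended as additional safety data became available to increase the duration of treatment with LASN01".
- SAP 10.1 makes the plan patient-specific: "The number of expected doses will depend on which protocol amendment the patient is consented to, regardless of study completion status".
- SAP 1 states: "A substantial number of patients did not reconsent to protocol v7.0/7.1, which led to the early termination of the study".
- SAP 16 opens its account of the changes with "Due to several consent withdrawals and patients declining to re-consent for the 12-month extension".

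Exposure is handled separately. SAP 10.2 says "Extent of treatment exposure for completed or discontinued patients will be calculated in days using the following", and the formula is last dose minus first dose plus one. It is summarised by arm, for pooled LASN01 and for all patients. SAP 7 tabulates study and treatment discontinuation by arm.

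The collection window is set in the protocol. Section 8.3.1 says "Detection and recording of AEs and SAEs starts from the signing of the ICF until the Day 365/Week 53 visit"; after that visit only treatment-related events are recorded, up to end of study (EOS). Section 7.2 asks that patients who stop drug remain on study.

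**The concern.** Safety compared with placebo is a primary objective. A crude percentage rises with the time a patient is watched, and so does an event count. If one arm has more patients with short follow-up, its percentage is lower at the same underlying rate, and nothing in the TEAE tables would show it.

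Randomisation balances the protocol version in expectation. Re-consent and withdrawal come after randomisation, however, and each arm has about 8 patients, so the realised mix of follow-up can differ. The All Patients column pools different durations even when the arms are perfectly balanced.

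SAP 16 adapts the efficacy analyses to the early termination (last observation carried forward, observed-data analyses, no per-protocol set). It lists no matching change for adverse events.

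**Working it through.** **1. Planned dosing span.** With four-weekly dosing, the last dose falls on day (doses − 1) × 28 + 1. For 13 doses this is 12 × 28 + 1 = 337, which reproduces the Day 337 in the documents. For 7 doses it is 6 × 28 + 1 = 169. The planned span therefore differs by a factor of 337/169 = 1.99.

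**2. Dosing days are not time at risk.** Under the current protocol, a patient who completes 13 doses has 337 dosing days. The window for any TEAE is 365 days (337/365 = 0.923, so dosing days are 8% short). The window for related TEAEs is 505 days (337/505 = 0.667, 33% short). For a patient who stops drug but stays on study the gap is wider.

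**3. Size of a between-arm effect.** The documents give no follow-up times, event rates for this trial or version mix by arm, so all of the following are assumptions:
- Follow-up of 196 days (7 × 28), 280 days (10 × 28) or 365 days. Only the 365-day window is in the documents, and the adverse event windows of earlier protocol versions are not given. Inclusion criterion 6 (Protocol 5.1) still refers to 36 weeks of treatment, which suggests an intermediate schedule but does not prove one.
- A constant hazard h of 0.3, 0.5 or 1.0 first events per patient-year, the same in both arms.
- 25% of one arm and 50% of the other on the shorter follow-up.

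The full gap between short (S) and long (L) follow-up is exp(−hS/365.25) − exp(−hL/365.25). The between-arm difference is that gap × (0.50 − 0.25).

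| S v L (days) | Full gap, points (h = 0.3 / 0.5 / 1.0) | × 0.25, points |
|---|---|---|
| 196 v 280 | 5.7 / 8.3 / 12.0 | 1.4 / 2.1 / 3.0 |
| 280 v 365 | 5.4 / 7.5 / 9.6 | 1.3 / 1.9 / 2.4 |
| 196 v 365 | 11.0 / 15.8 / 21.7 | 2.8 / 3.9 / 5.4 |

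One patient in 8 is 12.5 points. With an equal mix the multiplier, and so the difference, is zero.

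**4. Is a 25-point difference in mix plausible?** Suppose 8, 9, 10, 11 or 12 of the 24 randomised patients have short follow-up (assumed), spread purely by chance. By the hypergeometric distribution, the probability that placebo (8) and pooled LASN01 (16) differ by at least 25 points in the short share is 36%, 18%, 39%, 39% or 19% respectively. It is plausible, but not shown to have happened.

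**5. All Patients column.** One and the same rate gives a crude percentage of 1 − exp(−ht/365.25). For h = 0.3 to 1.0 this is 14.9% to 41.5% at 196 days, 20.5% to 53.5% at 280 days and 25.9% to 63.2% at 365 days.

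**6. Higher hazards.** Protocol 2.2.2.3 reports TEAEs in 35 of 58 healthy volunteers (60.3%), in a different population, including placebo, with follow-up not stated. If that follow-up was 8 or 12 weeks (assumed), h = −ln(1 − 0.603)/(56/365.25) ≈ 6.0, or with 84 days ≈ 4.0. The widest case (196 v 365 days) then shrinks to 0.9 or 2.4 points, because nearly everyone has an event. At an assumed 26 weeks it would be 5.3 points.

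**The case against.** The strongest reply is that no error has been shown. Allocation is 1:1:1, no passage reports an imbalance by arm, and the illustrated effect is below one patient in 8. The standard error of a difference between crude percentages of 40% and 50% with 8 per arm is √(0.4 × 0.6/8 + 0.5 × 0.5/8) = 0.247, about 25 points. Gross differences would also be visible already, since SAP 10.2 and SAP 7 tabulate exposure, completion and discontinuation by arm, and SAP 7 and SAP 10.1 list protocol version and doses received. All of this stands, and it limits the point to an optional improvement. It does not remove it: the existing tables give neither the right denominator nor a rate.

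A reader might infer that non-reconsent shortened observation on top of the 7-to-13-dose spread. The documents do not support counting it twice. Expected doses follow the version consented to, so declining the extension is largely a source of that spread. Withdrawal and early termination are the separate losses.

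A reader might also infer that the safety comparison is biased in favour of one arm. Nothing in the documents gives a direction or a split. The shortfall of dosing days against the collection window is the same for 13-dose completers in every arm, so it creates no between-arm bias by itself.

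Finally, the SAP's table list (Section 18) is not in the text available, so a planned exposure-adjusted table cannot be excluded. The point rests on the wording of SAP 12.1.

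**Conclusion.** The concern holds as a modest matter of interpretability. Follow-up varied between patients by the sponsor's own account, SAP 12.1 plans no time denominator, and the exposure table measures dosing days instead of adverse event time at risk.

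Under the assumptions above, the between-arm distortion is about 1 to 5 points. It is smaller if TEAE hazards are much higher and zero if the mix is equal. The one consequence that does not depend on chance imbalance is that the All Patients column averages over different durations. No hypothesis test is affected. Confidence is medium, because the observed follow-up, the earlier collection windows and the table list are not available.

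**What to change.** Keep the crude tables. Add one descriptive summary to SAP 12.1, by arm and for All Patients, with pooled LASN01 optional because the safety tables do not otherwise carry that column:
- total patient-years at risk;
- patients with a first event per 100 patient-years, for any TEAE, serious TEAE and TEAE leading to discontinuation.

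Time at risk runs from first dose to the earliest of first event, last contact, or the end of all-event collection under the patient's consented version (Day 365 under the current protocol). Only events inside that window count. If related TEAEs are included, their window runs to EOS or last contact, to match how they are recorded.

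The cost is a paragraph of SAP wording and one table. Protocol version, consent, dosing and event dates are already collected; the sponsor would need to state the collection cut-off of each earlier version. The downside is imprecision and reliance on a roughly constant hazard. For example, 3 patients with an event in 5.6 patient-years is 3/5.6 = 54 per 100 patient-years, with an exact Poisson 95% interval of 11 to 157. The rates should therefore be labelled descriptive and read beside the crude table.
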